1.3.2 Criteria for the selection of subjects

Inclusion Criteria:

Women ages 18 and older presenting for elective IUD insertion (any type of IUD, copper or hormonal); at an out-patient setting at Stanford; English speaking, and ability to give informed consent.

Exclusion Criteria:

- Pre-operative use of misoprostol
- Allergy to study medications (lidocaine)
- Known uterine anomaly
- Prior cervical surgery
- IV conscious sedation

1.3.3 Subject Recruitment and Allocation

Potential participants will be identified for recruitment if scheduled for IUD insertion (regardless of type) at the Stanford University Gynecology Clinic. They will be approached by the research coordinator or study investigator and consented for the study. If enrolled, they will be randomized by block randomization. The research coordinator will prepare a 20ml pre-filled syringe with either 2% lidocaine gel or placebo, so that the physician/researcher is blinded to the group allocated. Participants will receive the treatment previously allocated on a rolling bases. The patient and provider will be blinded as to the treatment group.

All patients will then receive instruction on how to properly self-insert the study medication using a pictorial guide as previously employed in a similar RCT at this site (SALSA).

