1.1.2 Objectives and hypotheses

The objective of this study is to compare pain control at various time points during IUD insertions using a locally applied, patient-administered lidocaine gel as compared to standard of care (i.e. no pre-procedural analgesia).

If a patient-administered vaginal gel is acceptable and effective, it would increase options for pain control during these gynecologic procedures.

Hypothesis: Patients who receive 20 mL of 2% lidocaine gel self-administered 20-30 minutes prior to IUD procedures will have pain control superior to that of a placebo gel.

Primary Outcomes

- SALUD (IUD Insertion): Pain perceived by Visual Analogue Scale (0-100 mm) at the time of speculum removal

Secondary Outcomes

- Pain perceived at additional time points during/after the procedure:
 - Anticipated pain: measured upon clinic intake
 - Baseline pain: upon arrival to procedure room
 - After speculum placement
 - After tenaculum placement

Note: The research coordinator will stand at the head of the bed beside the patient with an iPad that has an enlarged VAS on it. They will ask the patient to tap somewhere along the VAS at these various time points to indicate their respective pain score.

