1.2 Previous similar studies

While several previous studies have evaluated possible interventions for reducing IUD insertion pain, few have shown promising results. Although many providers recommend that patients take nonsteroidal anti-inflammatory drugs (NSAIDs) prior to the procedure, a 2009 Cochrane review concluded that NSAIDs are not effective at reducing pain during IUD insertion. The same review also concluded that the use of misoprostol to soften and open the cervix does not effectively reduce peri-insertional pain during insertion in nulliparous women, and may cause side effects. In a randomized trial, a 1% lidocaine paracervical block did not significantly decrease perceived pain with IUD insertion [Mody, 2012]. Randomized controlled trials by Allen et al. and McNicholas et al. examined the effect of 2% cervical lidocaine gel applied 3 minutes prior to the procedure. Both studies found no significant differences in pain scores with IUD insertion or tenaculum placement when compared with placebo.

To the best of our knowledge, there is no published data that 1) rigorously examines the effects of a prolonged time interval between local anesthetic administration and IUD insertion, or 2) explores whether adequate pain relief is possible through self-administered, non-invasive means alone.

In a soon to be published study conducted at Stanford (my primary fellowship project), self-administration of 20 ml of 2% lidocaine gel 20-30 minutes prior to first trimester surgical abortion was shown to be non-inferior to a traditional paracervical lidocaine block as a pain control approach. Given these promising results, we propose to

evaluate the effect of 2% lidocaine gel self-administered 20-30 minutes prior to IUD insertion in place of the standard of care pain management (i.e, no intervention).

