1.3.10 Data analysis

SAS Version 9.3 and SPSS Version 23.0 will be used for data analysis.

Statistical Methods:

- Demographic characteristics will be examined among the randomized groups using Fisher's exact test
- Median VAS pain scores will be analyzed with Student's *t*-tests and non-parametric tests, respectively
- Linear regression may be completed in multivariate analysis to identify predictors of pain in an exploratory analysis

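### The primary pain comparison uses no pre-treatment predictor of pain, so some precision is forgone that a pre-specified covariate model would recover at almost no cost

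*Combined protocol and SAP*

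**What the plan says.** The primary outcome (section 1.1.2) is "Pain perceived by Visual Analogue Scale (0-100 mm) at the time of speculum removal". The same section lists anticipated pain, taken at clinic intake, and baseline pain, taken on arrival in the procedure room, among the secondary outcomes.

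Eligibility (section 1.3.2) covers "any type of IUD, copper or hormonal", and no inclusion or exclusion criterion mentions parity. On allocation, section 1.3.3 says "If enrolled, they will be randomized by block randomization". It names no stratification factor.

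Section 1.3.10 assigns the VAS scores to t-tests and non-parametric tests without covariates. Demographics are compared between arms by Fisher's exact test, and no action follows from the result. The only model in the plan is this: "Linear regression may be completed in multivariate analysis to identify predictors of pain in an exploratory analysis". It names no covariates and is not directed at the treatment effect.

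**The concern.** The investigators expect pain to have predictors, since they plan to look for them. The population is also broad. If a characteristic known before treatment explains part of the spread in VAS, an unadjusted comparison leaves that part in the error term. The treatment difference is then estimated less precisely than the same patients would allow.

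At stake are the width of the confidence interval and, for effects smaller than the one in the sample-size summary, some power. There is a second, practical stake. With no covariates named beforehand, any adjusted result produced after a baseline imbalance has been seen will look chosen after the fact.

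**Working it through.** **Inputs.** From section 1.3.11: SD 21.7 mm, control mean 36.7 mm, experimental mean 21.7 mm (difference 15 mm), alpha 0.025 entered as alpha/2, power 90%, 200 patients before the 10% allowance. Equal allocation, 100 per arm, is assumed; the formula's factor of 2 implies it. R2 is the share of within-arm variance explained by the covariates. No document gives it, so 0.05 to 0.20 is an assumption.

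**The plan's own figure.** n per arm = f(alpha/2, beta) x 2 x SD^2 / difference^2 = 12.41 x 2 x 21.7^2 / 15^2 = 51.9, so 52 per arm and 104 in total. At two-sided 0.05 it is 44 per arm, 88 in total. Neither gives 200. A difference of 10 mm at two-sided 0.05 gives 99 per arm, 198 in total, but section 1.3.11 does not state that difference. The listed effect of 15% would be 0.15 x 36.7 = 5.5 mm if taken relative to the control mean. The mismatch is a separate matter. It bears on this point only because it leaves the target effect uncertain, so 15, 10 and 5.5 mm are all shown.

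**Precision.** Unadjusted SE = 21.7 x sqrt(2/100) = 3.07 mm. Adjusted SE = 3.07 x sqrt(1 - R2). Equivalent unadjusted sample size = 200/(1 - R2). Power = Phi(difference/SE - 2.241), where 2.241 is the normal quantile for two-sided 0.025.

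| R2 (assumed) | SE, mm | 200 patients worth | Power, 15 mm | Power, 10 mm | Power, 5.5 mm |
|---|---|---|---|---|---|
| 0 (unadjusted) | 3.07 | 200 | 99.6% | 84.5% | 32.7% |
| 0.05 | 2.99 | 211 | 99.7% | 86.5% | 34.4% |
| 0.10 | 2.91 | 222 | 99.8% | 88.4% | 36.3% |
| 0.20 | 2.75 | 250 | 99.9% | 92.0% | 40.7% |

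**What such an R2 would take from parity alone.** Assume half the women are nulliparous and their mean pain differs by d. Then R2 = 0.25 x d^2 / 21.7^2. For d of 5, 10, 15 and 20 mm this gives 0.013, 0.053, 0.119 and 0.212, and 200 patients are worth about 203, 211, 227 and 254. All four values of d are assumptions.

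**Chance imbalance is the same loss, not an extra one.** At 100 per arm, the difference between arms in the proportion nulliparous has SD sqrt(2 x 0.25/100) = 7.1 percentage points. With d = 10 mm it contributes 0.71 mm, or variance 0.50, to the unadjusted difference. The total variance is 3.07^2 = 9.42. Removing 0.50 leaves 8.92, an SE of 2.99 mm, which is what R2 = 0.053 gives directly. A two-SD imbalance (14 points) would move the estimate by 1.4 mm, less than half of one standard error.

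**The case against.** The strongest case against is that an unadjusted comparison after block randomisation is a legitimate primary analysis, and that adjustment buys almost nothing at the plan's stated effect. Both statements are true. At 15 mm, power is already 99.6%. The useful gain appears only if the real target is smaller and the covariates are reasonably prognostic.

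Several stronger readings are tempting, and the documents do not support them:

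- *The plan itself shows that parity predicts pain.* It does not. Section 1.2 reports a cited review's finding that misoprostol "does not effectively reduce peri-insertional pain during insertion in nulliparous women". That concerns a drug this trial excludes and does not compare pain by parity. The reference list adds only the title of a trial in nulliparous women.
- *IUD type should have been adjusted for.* The documents say that any type is eligible and nothing about whether type affects pain.
- *Chance imbalance makes the primary test unsound.* It does not. Randomisation preserves the type I error, and the variance from imbalance is already inside the 3.07 mm.
- *Lack of stratification is a defect.* Covariate adjustment recovers the precision without it.

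It is also fair to say that section 1.3.10 leaves a more basic gap, since it does not settle which single test is primary. The proposal below closes that gap too.

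What survives is a modest point: the plan already collects one plausible covariate before treatment and makes no use of it in the treatment comparison.

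**Conclusion.** The point holds as an inexpensive improvement, not as an error. The planned comparison is valid but forgoes whatever precision pre-treatment predictors of pain could supply. With an assumed R2 of 0.05 to 0.20, the standard error falls by about 2.5% to 11%. Power is practically unchanged for a 15 mm effect and rises by about 2 to 7.5 percentage points for a 10 mm effect.

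These figures rest on 100 analysed patients per arm, an SD of 21.7 mm and a normal approximation. The R2 range comes from no document, and confidence in the actual size of the gain is therefore low. If the covariates are not prognostic, nothing is gained, and the cost is two residual degrees of freedom (198 to 196).

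**What to change.** In section 1.3.10, define the primary analysis as a linear model of VAS at speculum removal on arm, reporting the adjusted mean difference with its confidence interval, with two covariates named in advance:

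- anticipated pain at clinic intake, which section 1.1.2 already collects; state that it is recorded before randomisation;
- parity (nulliparous or parous), recorded at intake.

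Do not use the procedure-room baseline score as a covariate. The gel is self-administered 20-30 minutes before the procedure, so that score may be taken after treatment.

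Keep the unadjusted comparison as a sensitivity analysis and the predictor regression as exploratory. Adjusting for the IUD type planned at intake, or blocking within parity strata if the allocation list is not yet made, is optional and not needed for the gain.

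The cost is one model line, and one intake field if parity is not already among the demographics recorded, which the documents do not show. The one constraint is that the covariates and their coding must be fixed before outcome data are examined by arm.

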1.3.4 Description of the drugs and devices to be studied

Xylocaine (lidocaine HCl) is a common local anesthetic that works by stabilizing the neuronal membrane by inhibiting the ionic fluxes required for the initiation and conduction of impulses. Local anesthetics of the amide type are thought to act within the sodium channels of the nerve membrane. According to the packaging insert, anesthesia is achieved within 5 minutes, depending on the area of application, and duration of anesthesia is approximately 20-30 minutes. It is used prior to many genitourinary procedures involving mucus membranes including the urethra, anus, and vulva. While no recommended dose is known for vaginal use prior to surgical abortion, recommended doses are known for the following procedures: 20 ml for proctoscopy/anoscopy; 10 ml for female urethral anesthesia as in cystoscopy. A single maximum dosage for 2% Xylocaine jelly is not established [Blanco 1982], however Lexicomp drug information for topical lidocaine jelly cites a maximum dose of 600 mg in any 12-hour period.

The serum toxicity of intracervical lidocaine is thought to be around 5 ug/ml [Blanco 1982] and a study looking at serum lidocaine levels 10 minutes after paracervical injection of 20 ml of 1% lidocaine (200 mg total) found mean blood levels of 0.9 to 1.61 ug/ml [McKenzie 1978].

Similarly, a study investigating vaginal anesthesia with 4ml of 10% lidocaine spray (400mg total) 5 minutes prior to high dose intracavitary brachytherapy found a significant decrease in procedural pain [Chen 1998]. This study also looked at serum lidocaine levels at various time points following administration and found that the 400mg dose never reached toxic levels in participants. These data are further supported by non-toxic levels seen after nasopharyngeal and oropharyngeal application in the studies cited above.

Based on this information, participants in the lidocaine gel group will self-administer 20 ml of 2% lidocaine HCl vaginally (400 mg total) 20-30 minutes prior to the start of the procedure. We are allowing a window of time to account for real life clinic practice and possible delays.

The product:

- XYLOCAINE® JELLY 2% (lidocaine hydrochloride) AstraZeneca
 - 20 mL (20 mg/mL) – 400mg total

Control Groups:

SALUD (IUD Insertion Arm):

No Intervention Group: As an alternative to lidocaine gel, participants will receive no intervention for pain management for IUD insertion (standard of care), but will receive placebo gel (standard lubricating gel).

1.3.6 Follow-up procedure

There is no extended follow-up planned for this study. Subjects will complete a survey at the completion of the procedure asking them to give a final pain score (secondary outcome) and assessment of overall acceptability (likelihood to recommend procedure or choose this form of pain control again). Any potential procedural complications will be managed using typical standard of care procedures for this clinic.

1.3.7 Criteria for discontinuation

Subjects will be able to withdraw from the study at any point during the procedure should they so choose.

1.3.8 Laboratory and other investigations

Not-applicable.

1.3.9 Data management

Data management will be done using RedCap, an electronic data capture program, and performed by the research coordinator and primary investigator (fellow).

1.3.10 Data analysis

SAS Version 9.3 and SPSS Version 23.0 will be used for data analysis.

Statistical Methods:

- Demographic characteristics will be examined among the randomized groups using Fisher's exact test
- Median VAS pain scores will be analyzed with Student's *t*-tests and non-parametric tests, respectively
- Linear regression may be completed in multivariate analysis to identify predictors of pain in an exploratory analysis

1.3.11 Number of subjects and statistical power

SALUD (IUD Insertion): The following power calculation accounts for continuous outcomes in a superiority trial

$$n = f(\alpha/2, \beta) \times 2 \times \sigma^2 / (\mu_1 - \mu_2)^2$$

- Effect size = 15% difference in VAS [Jensen 2003, Todd 1996, Rowbothom 2001]

- Mean outcome in control group: 36.7mm [Allen 2013]
- Standard deviation of VAS = 21.7mm [Allen 2013]
- Assuming $\alpha = 0.025$, $\beta = 0.10$, 90% power

SUMMARY: 200 patients are required to have a 90% chance of detecting, as significant at the 2.5% level, a decrease in the primary outcome measure from 36.7 in the control group to 21.7 in the experimental group. Accounting for drop-outs and protocol deviations by adding 10% to the number of participants, the total enrollment will be 220.

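### The stated 200 patients does not follow from section 1.3.11's own formula and inputs, which give 104

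*Combined protocol and SAP*

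**What the plan says.** Section 1.3.11 (Number of subjects and statistical power) sets out a full calculation for comparing two means in a superiority trial. The number n is f(α/2, β) times 2σ², divided by the squared difference in means. The inputs are:

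- alpha 0.025, beta 0.10, power 90%;
- "Standard deviation of VAS = 21.7mm";
- a control mean of 36.7 mm;
- "Effect size = 15% difference in VAS".

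The summary concludes that "200 patients are required to have a 90% chance of detecting, as significant at the 2.5% level", a decrease "from 36.7 in the control group to 21.7 in the experimental group". Drop-outs and protocol deviations are then covered "by adding 10% to the number of participants, the total enrollment will be 220".

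The primary outcome in section 1.1.2 is "Pain perceived by Visual Analogue Scale (0-100 mm) at the time of speculum removal". Section 1.3.10 plans both t-tests and non-parametric tests for the pain scores.

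**The concern.** Every quantity the formula needs is printed, so the total should be reproducible by hand. It is not: the result is close to half of 200. A gap of that size is not rounding, so the sample size, power, difference and SD cannot all be as stated.

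The direction is towards too many patients, so the ability to detect 15 mm is not at risk on the printed figures. Two other things are at stake.

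- **What the trial is designed to detect.** This bears on how a small or null result is read. A trial with 90% power for 15 mm and one with 90% power for about 11 mm support different conclusions.
- **Justification of enrolment.** Either nearly twice the computed number of patients is to be randomised without a stated reason, or a design assumption is misprinted.

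**Working it through.** **Inputs (all from section 1.3.11).** σ = 21.7 mm; μ₁ − μ₂ = 36.7 − 21.7 = 15.0 mm; α = 0.025; β = 0.10. No allocation ratio is stated. Equal arms are assumed, because the factor 2 in the formula implies them.

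**Attempt to reproduce the 200.** The formula splits alpha, so read literally it is a two-sided 2.5% test:

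- f(0.0125, 0.10) = (2.2414 + 1.2816)² = 12.411
- n = 12.411 × 2 × 21.7² / 15² = 12.411 × 2 × 470.89 / 225 = 51.95, so 52 per arm and **104 in total**

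If 0.025 is already the one-sided level:

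- f = (1.9600 + 1.2816)² = 10.507
- n = 10.507 × 2 × 470.89 / 225 = 43.98, so 44 per arm and **88 in total**

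Neither gives 200.

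**Other readings** (two-sided 2.5%, 90% power and SD 21.7 mm unless noted):

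| Reading | Total |
|---|---|
| Exact t-test (53.2, so 54 per arm) | 108 |
| Exact t-test, one-sided 2.5% (44.96, so 45 per arm) | 90 |
| Rank test at worst-case efficiency: 51.95 / 0.864 = 60.1, so 61 per arm | 122 |
| 95% power instead of 90% | 128 |
| 2:1 allocation | 117 |
| 3:1 allocation | about 140 |
| Bonferroni correction over six tests | 144 |
| 15% taken relative to 36.7 mm, i.e. 5.5 mm (386 per arm) | 772 |

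The relative reading overshoots and contradicts the printed experimental-arm mean of 21.7 mm. Reading 200 as a per-arm number is ruled out, because total enrolment is 220.

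**Drop-out allowance.** The 10% is applied after the 200 (200 × 1.10 = 220), so it cannot be part of it. On the computed totals it gives 104 × 1.10 = 114.4, so 115 enrolled, or 88 × 1.10 = 96.8, so 97. The planned 220 is 220 / 115 = 1.9 times the first of these.

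**What 200 evaluable patients deliver on the printed SD (100 per arm):**

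| | Two-sided 2.5% | One-sided 2.5% |
|---|---|---|
| Power for 15 mm (t-test) | 99.6% | 99.8% |
| Difference at 90% power, normal approximation | √(12.411 × 2 × 470.89 / 100) = 10.8 mm | 9.9 mm |
| Difference at 90% power, t-test | 10.9 mm | 10.0 mm |

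**What would give about 200.** These are illustrations; the documents support none of them. For 15 mm, 100 per arm corresponds to an SD of 15 / √(12.411 × 2 / 100) = 30.1 mm at two-sided 2.5%, or 32.7 mm at one-sided 2.5%. With SD 21.7 mm, a 10 mm difference at one-sided 2.5% needs 98.96, so 99 per arm and 198 in total.

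**The case against.** The best defence is that the consequence is mild. On the printed inputs the promised 90% power is exceeded, and neither the type I error rate nor the validity of the comparison suffers. If instead an input was misprinted, for example the SD, 200 may be right for 15 mm and only one printed number is at fault. This stands, and it limits the point to reproducibility and justification.

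The recruitment estimate also fits the larger number. Section 1.3.13 expects over 100 procedures a month with 30% enrolment, about 30 patients a month, and 220 / 30 is about 7.3 months, within the stated 7 to 10. That makes a simple misprint of the total less likely. It also argues against cutting enrolment on the strength of an SD that may itself be wrong. Both are fair, and they are why tracing the calculation comes first.

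Smaller points:

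- The 15% label is loose wording, not a second arithmetic error: 15% of a 0-100 mm scale is 15 mm, and the printed means agree.
- Reading f(α/2, β) with alpha 0.025 as two-sided 2.5% is natural, so stating the sidedness is a clarification. The mismatch exists either way.
- The 0.864 efficiency bound assumes a pure shift between arms, which a bounded pain score may not follow. Closing the gap would, however, need an efficiency of about 51.95 / 100 = 0.52, and section 1.3.11 mentions no such adjustment.

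None of this makes 200 follow from the printed inputs.

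**Conclusion.** The concern holds. As printed, section 1.3.11 is internally inconsistent: its formula and inputs require 104 patients (88 if 2.5% is one-sided), and it states 200. The result assumes equal arms, but the unequal allocations tried do not reach 200 either. The arithmetic is certain. What cannot be settled from the documents is which of sample size, power, difference and SD departs from the value used.

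This should be fixed, but it does not threaten the validity of the trial, and on the printed inputs there is no shortage of patients for a 15 mm difference.

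**What to change.** Correct section 1.3.11 as follows:

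1. Find the SD and the difference that were actually used to obtain 200, print them, and show the calculation.
2. Write the target as 15 mm (15 points on the 0-100 mm scale) instead of 15%.
3. State whether the 2.5% level is one-sided or two-sided, and that allocation is equal if that is intended.
4. Restate what 200 evaluable patients deliver. If the printed inputs are confirmed and 2.5% is two-sided, the sentence should say about 90% power for a difference of 10.8 mm and more than 99% for 15 mm.
5. Only once the inputs are confirmed, either give a reason for enrolling about twice the computed number or reduce it.

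If the calculation turns out to have used another SD or difference, replacing the misprinted value may be all that is needed.

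The cost is a correction of numbers and wording in one section, with no extra patients. Enrolment could fall if the printed inputs prove right.
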